3.2. CHANGES TO ANALYSES FROM PROTOCOL

- Section 14.5.4 of the protocol indicates that laboratory analytes will be summarized descriptively as value and change from baseline, as well as shifts from baseline (based on low, normal, high categorization) at each visit. To allow for more focused presentation of values most likely to represent a safety concern, laboratory analytes will be summarized as shift from the baseline to the worst post-baseline category (based on National Cancer Institute [NCI] Common Terminology Criteria for Adverse Events [CTCAE] v 4.03 severity grades).
- In the protocol, PFS is to be summarized using 90% and 95% CIs. However, to be consistent and following standard analyses, PFS will be summarized using % CIs.
- In the protocol, ORR is to be summarized using 80%, 90% and 95% CIs. However, to be consistent and following standard analyses, ORR will be summarized using 95% CIs. In addition, it was indicated that the 95% CI would be done only for expansion phase cohorts with at least 20 patients, however the 95% CI would be provided for all expansion phase cohorts.
- No subgroup analyses were planned in the protocol, however, to assess the possible effect of tazemetostat on previously irradiated lesions, a subgroup analysis of ORR by prior radiotherapy

(Yes vs No) will be performed for the expansion phase by cohort and overall, and for the entire study by dose level and overall.

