 - c. FDG-PET may be used to upgrade a response to a CR in a manner similar to a biopsy in cases where a residual radiographic abnormality is thought to represent fibrosis or scarring. The use of FDG-PET in this circumstance should be prospectively described in the protocol and supported by disease-specific medical literature for the indication. However, it must be acknowledged that both approaches may lead to false positive CR due to limitations of FDG-PET and biopsy resolution/sensitivity.

Note: A ‘positive’ FDG-PET scan lesion means one which is FDG avid with an uptake greater than twice that of the surrounding tissue on the attenuation corrected image.

Disease Evaluation Guidelines

Measurable Disease

Measurable lesions are defined as those that can be accurately measured in at least one dimension (longest diameter to be recorded) as:

- ≥ 20 mm (≥ 2 cm) by chest X-ray
- ≥ 10 mm (≥ 1 cm) with CT scan, MRI, or calipers by clinical exam

Note: Tumor lesions that are situated in a previously irradiated area might or might not be considered measurable.

Malignant lymph nodes (LN) can be considered pathologically enlarged and measurable, a LN must be ≥ 15 mm (≥ 1.5 cm) in short axis when assessed by CT scan (CT scan slice thickness recommended to be no greater than 5 mm [0.5 cm]). At baseline and follow-up, only the short axis will be measured and followed.

Non-Measurable Disease

All other lesions (or sites of disease), including small lesions (longest diameter < 10 mm [< 1 cm] or pathological LN with ≥ 10 to < 15 mm [≥ 1 to < 1.5 cm] short axis), are considered non-measurable disease. Bone lesions, leptomeningeal disease, ascites, pleural/pericardial effusions, lymphangitis cutis/pulmonitis, inflammatory breast disease, and abdominal masses (not followed by CT or MRI), are considered as non-measurable.

Note: Cystic lesions that meet the criteria for radiographically defined simple cysts should not be considered as malignant lesions (neither measurable nor non-measurable) since they are, by definition, simple cysts.

‘Cystic lesions’ thought to represent cystic metastases can be considered as measurable lesions, if they meet the definition of measurability described above. However, if non-cystic lesions are present in the same subject, these are preferred for selection as target lesions.

Target Lesions

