4.4. SAMPLE SIZE

Dose Escalation: The sample size is not based on a statistical consideration. The number of subjects will be determined based in part on the number of dose escalations required to determine the protocol defined MTD and/or RP2D. It is expected that up to approximately 48 subjects will be enrolled with the "Rolling 6" dose-escalation design (subjects who discontinue in absence of a DLT prior to the completing of the DLT evaluation period may be replaced).

The MTD and RP2D are defined as the dose level below which >1 subject of 3 or ≥ 2 subjects of 6 experience a DLT on the dose-escalation portion of the study during Cycle 1. In the event that MTD is not reached, the RP2D will be that dose that results in a mean $AUC_{(0-24)}$ of at least 5900 ng•h/mL (~80% of the mean value observed after administration of 800 mg BID in adults) or provides biologic and/or clinical activity in subjects in this study.

Dose Expansion: The sample size for dose expansion (Cohorts 1 to 3) is based on the hypothesized improvement in ORR over historical rates. An ORR no higher than 5% would

have no clinical benefit over existing therapies; an ORR of 20% is considered of clinical interest. For each dose expansion cohort separately, using a one-sided test and targeting a Type I error rate of 10% and a Type II error rate of 20% requires 20 pediatric subjects to be enrolled per cohort, in Cohorts 1 to 3. To establish that the data support tazemetostat, at least 3 of 20 subjects will be required to have an objective response (i.e., an observed 15% ORR) within a cohort. Due to the discrete nature of the primary endpoint, this statistical test achieves a Type I error rate of 8% (i.e., probability of deciding for tazemetostat when the true ORR is 5%), and a Type II error rate of 21% (i.e., probability of deciding against tazemetostat when the true ORR is 20%). Twelve subjects were to be enrolled in dose expansion Cohort 4 to evaluate the PK of tazemetostat when administered as a tablet formulation to pediatric subjects. Sufficient information to describe the PK of tazemetostat was obtained after administration of tazemetostat tablets to 4 pediatric subjects. Therefore, Cohort 4 was closed to further enrolment. Approximately 72 subjects will be enrolled across the 4 Dose Expansion cohorts.

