13.1. PRIOR ANTI-CANCER THERAPY AND RADIOTHERAPY

Prior anti-cancer therapy and radiotherapy will be summarized and listed for the ITT population. The summary for prior anti-cancer therapies will include:

- Number of regimens (descriptive statistics and by category: 0, 1, 2, or more than 2 prior regimens)
- Number of regimens in the advanced/metastatic setting (0, 1, 2, or more than 2 prior regimens)
- Number of prior lines (descriptive statistics and by category: 0, 1, 2, 3, 4, or more than 4 prior lines)
- Therapy setting (Neoadjuvant, Adjuvant, Therapeutic for Advanced/Metastatic Disease, Consolidation, Maintenance, or Unknown); A subject may be counted in multiple

categories

- Incidence of prior anti-cancer therapies by WHO Drug ATC level 4 and preferred drug name
- Time from last PD to study entry
- Time for last anti-cancer treatment to study entry
- Best response

The summary for the prior radiotherapy will include:

- Number of prior courses (descriptive statistics and by category: 0, 1, or 2 or more courses)
- Sites of prior radiotherapy. A subject may be counted in multiple categories
- Type of radiation (total body irradiation, total marrow irradiation, proton therapy, radio surgery, gamma knife, other) by frequency.

Prior radiotherapy is defined as radiotherapy performed on or prior to the date of first dose of study drug. Partial dates that cannot conclusively be identified as occurring after the start of treatment will be assumed to have occurred prior to start of treatment.

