15.1. OBJECTIVE RESPONSE RATE AND DURATION OF RESPONSE

Best Overall Response (BOR)

The summaries of BOR will include number and percentage of subjects in each of these categories:

- Complete response (CR)

- Partial response (PR)
- Stable disease (SD)
- Progressive disease (PD)
- Not Evaluable (NE)
- Unknown/Missing

Confirmation of CR/PR is required at least 28 days after the initial CR/PR was first met. Subjects will be evaluated for response based on the following disease appropriate criteria:

- For CNS tumors, response will be assessed based on RANO (Wen PY, 2010).
- Solid tumors will be assessed based on RECIST version 1.1 (Eisenhauer EA, 2009).

Objective Response Rate

ORR is defined as the percentage of subjects achieving a confirmed CR or PR from the start of tazemetostat until PD or the start of subsequent anti-cancer therapy, whichever is earlier, according to the appropriate disease evaluation criteria.

Subjects with not evaluable, unknown or missing best response will be handled as non-responders, i.e. they will be included in the denominator when calculating the ORR.

For dose escalation, ORR (secondary endpoint) will be summarized by dose level and overall.

For dose expansion, ORR (primary endpoint) will be summarized by cohort and overall. An exact 95% binomial CI for ORR in each cohort and overall will be provided as well.

In addition, ORR will be summarized by dose level across the dose escalation and dose expansion phases and overall. For each dose level and overall, an exact 95% CI for ORR will be calculated.

Also, a subgroup analysis of ORR by prior radiotherapy (Yes vs No) will be performed for the expansion phase by cohort and overall, and for the entire study by dose level and overall.

A plot of the maximum percent tumor reduction from baseline in target lesions for each subject will be provided.

Duration of Response

DOR will be calculated only for subjects with a confirmed CR or PR. DOR is defined as the interval of time from the first documented evidence of confirmed CR or PR until the first

documented PD or death due to any cause, whichever occurs first.

DOR censoring rules will follow those of the PFS analysis defined in **Table 3** below.

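### The prior-radiotherapy subgroup is a per-subject Yes/No split and does not reliably answer its stated question about previously irradiated lesions

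*SAP*

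**What the plan says.** SAP 3.2 lists this subgroup among the changes from the protocol and gives its purpose: "to assess the possible effect of tazemetostat on previously irradiated lesions, a subgroup analysis of ORR by prior radiotherapy". SAP 6.1 repeats it, and SAP 15.1 specifies it: "Also, a subgroup analysis of ORR by prior radiotherapy (Yes vs No) will be performed for the expansion phase by cohort and overall". It is also planned for the whole study, by dose level and overall.

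The classifying variable comes from SAP 13.1: "Prior radiotherapy is defined as radiotherapy performed on or prior to the date of first dose of study drug". Field, lesion and target status play no part. The same section plans a summary of "Sites of prior radiotherapy. A subject may be counted in multiple categories".

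The endpoint is also per subject: "ORR is defined as the percentage of subjects achieving a confirmed CR or PR from the start of tazemetostat until PD". The only planned display of target-lesion change is per subject too: "A plot of the maximum percent tumor reduction from baseline in target lesions for each subject will be provided". It carries no marker for irradiation.

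On whether irradiated lesions can be target lesions, Protocol Appendix 4 (RECIST 1.1) notes: "Tumor lesions that are situated in a previously irradiated area might or might not be considered measurable". No other section settles this. Appendix 5 (RANO, used for CNS tumors) has no corresponding note.

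**The concern.** The stated question is about lesions that were irradiated before entry. The planned variable records whether the subject ever had radiotherapy. The two agree only if nearly every Yes subject has the target lesions inside the irradiated area.

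Two kinds of subject break the agreement:

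- A subject irradiated at a site with no current target lesion is a Yes but contributes nothing about irradiated lesions.
- A subject with both irradiated and non-irradiated target lesions is a Yes, but the response reflects both kinds.

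The No group has no irradiated lesions by definition, so the mixing is confined to the Yes group.

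What is at stake is interpretation. A small or absent Yes/No difference could be read as showing that prior irradiation of the lesion does not matter, and a large one as showing that it does. Neither reading would be safe.

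**Working it through.** **The plan's own figure.** The concern contests no stated number. The ORR rates used below come from SAP 4.4, so that section's rule was checked first. With n = 20 and success at 3 or more responses, the exact binomial gives:

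- P(X ≥ 3 | p = 0.05) = 0.0755, stated as 8%.
- P(X ≤ 2 | p = 0.20) = 0.2061, stated as 21%.

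Both reproduce.

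**Inputs for the illustration**

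- Two ORR levels, 5% and 20%, from SAP 4.4 ("an ORR of 20% is considered of clinical interest"; 5% is the rate regarded as no benefit). They serve only as a convenient 15-point contrast. The plan does not claim this difference between irradiated and non-irradiated lesions.
- m, the share of Yes subjects with no irradiated target lesion. It is not in the documents, so 0% to 100% is shown.
- pI, the ORR in Yes subjects with irradiated target lesions.
- pN, the ORR in No subjects.
- pH, the ORR in Yes subjects without an irradiated target lesion.

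**Formula**

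Observed Yes minus No = (1 − m)(pI − pN) + m(pH − pN).

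**Case 1: pH = pN (assumed).** The second term vanishes and the contrast is (1 − m) × 15 points in size. With pI = 20% and pN = 5%:

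| m | ORR in Yes group | Observed difference |
|---|---|---|
| 0% | 20.00% | 15.00 points |
| 25% | 0.75 × 20 + 0.25 × 5 = 16.25% | 11.25 points |
| 50% | 0.50 × 20 + 0.50 × 5 = 12.50% | 7.50 points |
| 75% | 0.25 × 20 + 0.75 × 5 = 8.75% | 3.75 points |
| 100% | 5.00% | 0 points |

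With the rates reversed (pI = 5%, pN = 20%), the differences have the same size and the opposite sign.

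**Case 2: pH differs from pN.** Prior radiotherapy may track tumor type and earlier treatment, so equal ORR is not assured. Take m = 50%:

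- No lesion effect (pI = pN = 5%) but pH = 20%: 0.5 × 0 + 0.5 × 15 = +7.5 points, a spurious difference.
- No lesion effect (pI = pN = 20%) but pH = 5%: 0.5 × 0 + 0.5 × (−15) = −7.5 points.
- Lesion effect present (pI = 20%, pN = 5%) and pH = 20%: 0.5 × 15 + 0.5 × 15 = 15 points, so no attenuation.

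Dilution is therefore one possible outcome and not the only one.

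**Precision.** Assume a cohort of 20 splits 10/10 (the documents give no split). Exact 95% intervals for ORR are 0% to 30.8% for 0/10, 0.3% to 44.5% for 1/10, and 2.5% to 55.6% for 2/10. Within one cohort, differences of the size shown above could hardly be told apart under either classification.

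**The case against.** The strongest reply is that this is an added, descriptive subgroup with no test or decision attached, and that ORR is a subject-level endpoint, so any ORR split must be made per subject. Both points are correct. It follows that a flag for at least one irradiated target lesion would still mix lesions within a subject: one irradiated lesion among up to five would set the flag, while RECIST response is judged on summed diameters. A useful flag has to be graded, and only change per lesion answers a lesion-level question directly.

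A second reply is that Yes/No may be a fair proxy if most Yes subjects have their target lesions in the irradiated area. That is possible, and the documents do not exclude it. A reader might infer that the subgroup cannot answer its question at all, but the unknown m does not support so strong a claim.

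A third reply concerns feasibility. SAP 13.1 shows that radiotherapy sites will be summarized, but not that they are recorded finely enough to match to single lesions. SAP 11 plans the primary tumor's location at diagnosis and counts and sizes of target lesions, but not their locations. For CNS tumors, a coarse site might add little to Yes/No. This stands, and the eCRF has to be checked.

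A reader might also infer that the subgroup was added to detect delayed radiation effects that look like response. SAP 3.2 does not say so; it names a drug effect on irradiated lesions. Protocol 4.2 also sets minimum intervals since radiotherapy (14 days, 21 days or 12 weeks, by type) and requires relapsed or refractory disease. The mismatch between aim and variable does not depend on that motive.

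**Conclusion.** The point holds as a mismatch between a lesion-level aim and a subject-level variable. Followed exactly, the plan gives a contrast by radiotherapy history that does not reliably describe previously irradiated lesions.

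Its size cannot be fixed from the documents. Under the stated assumptions, a 15-point difference shrinks to between 11.25 and 3.75 points as m goes from 25% to 75%. This rests on two things the documents do not give: the value of m, and equal ORR in No subjects and in Yes subjects without an irradiated target lesion. A reader might infer that the contrast is bound to be biased toward no difference. If the second assumption fails, it can move either way.

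The consequence is limited. The primary ORR analysis, the sample size and the 3-of-20 rule are unaffected. This is a low-priority improvement, worth making because it is cheap and prevents a misreading.

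**What to change.** Before database lock, which SAP 1 already requires ahead of the analyses:

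1. Check in the eCRF whether target-lesion location and radiotherapy site are recorded finely enough to match.
2. If they are, classify each subject by target lesions at a previously irradiated site: all, some, none or unknown. Report ORR descriptively by that flag, and mark it on the tumor-reduction plot already planned in SAP 15.1.
3. Where feasible, show the change in each target lesion by irradiation status.
4. Keep the Yes/No table only as a summary by radiotherapy history.
5. If the recorded sites are too coarse, reword the aim in SAP 3.2 as ORR by prior radiotherapy history, and draw no conclusion about irradiated lesions.

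The cost is some programming and a data review. Matching will be approximate where the radiation field is not known exactly, and the four categories will be smaller than the two they replace. Rewording alone needs no new data work.

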4. PLANNED ANALYSES AND SAMPLE SIZE

4.1. INTERIM ANALYSIS

Dose Escalation: The CSRC will review available safety data, PK and tazemetostat exposure data from each dose level cohort to make recommendations regarding dose escalation in subsequent cohorts.

Dose Expansion: No interim analysis will be performed.

4.2. PRIMARY ANALYSIS

The primary analysis for each cohort of the study may occur separately when each cohort has at least met its primary objective (further described in Section 15.1). Details regarding the timing of the PK, PD, genetics, and cellular pharmacologic analyses will be described in detail under separate SAPs.

4.3. FINAL ANALYSIS OF PROGRESSION-FREE SURVIVAL AND OVERALL SURVIVAL

Depending on the maturity of PFS and OS data at the time of the primary analysis, analyses of PFS and OS may be repeated when data are mature.

4.4. SAMPLE SIZE

Dose Escalation: The sample size is not based on a statistical consideration. The number of subjects will be determined based in part on the number of dose escalations required to determine the protocol defined MTD and/or RP2D. It is expected that up to approximately 48 subjects will be enrolled with the "Rolling 6" dose-escalation design (subjects who discontinue in absence of a DLT prior to the completing of the DLT evaluation period may be replaced).

The MTD and RP2D are defined as the dose level below which >1 subject of 3 or ≥ 2 subjects of 6 experience a DLT on the dose-escalation portion of the study during Cycle 1. In the event that MTD is not reached, the RP2D will be that dose that results in a mean $AUC_{(0-24)}$ of at least 5900 ng•h/mL (~80% of the mean value observed after administration of 800 mg BID in adults) or provides biologic and/or clinical activity in subjects in this study.

Dose Expansion: The sample size for dose expansion (Cohorts 1 to 3) is based on the hypothesized improvement in ORR over historical rates. An ORR no higher than 5% would

have no clinical benefit over existing therapies; an ORR of 20% is considered of clinical interest. For each dose expansion cohort separately, using a one-sided test and targeting a Type I error rate of 10% and a Type II error rate of 20% requires 20 pediatric subjects to be enrolled per cohort, in Cohorts 1 to 3. To establish that the data support tazemetostat, at least 3 of 20 subjects will be required to have an objective response (i.e., an observed 15% ORR) within a cohort. Due to the discrete nature of the primary endpoint, this statistical test achieves a Type I error rate of 8% (i.e., probability of deciding for tazemetostat when the true ORR is 5%), and a Type II error rate of 21% (i.e., probability of deciding against tazemetostat when the true ORR is 20%). Twelve subjects were to be enrolled in dose expansion Cohort 4 to evaluate the PK of tazemetostat when administered as a tablet formulation to pediatric subjects. Sufficient information to describe the PK of tazemetostat was obtained after administration of tazemetostat tablets to 4 pediatric subjects. Therefore, Cohort 4 was closed to further enrolment. Approximately 72 subjects will be enrolled across the 4 Dose Expansion cohorts.

5. ANALYSIS POPULATIONS

The **Intent-to-Treat (ITT) population** consist of all subjects who receive at least one dose of tazemetostat. The ITT population will be used for summaries and analysis of demographics, baseline disease characteristics, prior treatment, surgical and medical history and efficacy endpoints.

The **Safety population** consist of all subjects in the ITT population who have at least one post-dose safety observation recorded. The Safety population will be used for summaries and analysis of safety and tolerability.

The **Dose-Limiting Toxicity (DLT) Population** will consist of all dose escalation subjects in the Safety Population who:

- Experience a DLT during Cycle 1 as defined in Protocol Section 6.3
OR
- Are not removed from Cycle 1 for reasons other than toxicity and did not have an interruption in study treatment for more than 14 days during Cycle 1

6. GENERAL CONSIDERATIONS

6.1. GROUPING OF SUBJECTS AND TABLE PRESENTATION

Subjects will be grouped and summarized by dose level for the escalation phase, by cohort for the expansion phase and by overall for each study phase. In addition, ORR will be summarized by dose level and overall across the dose escalation and expansion phases. Also, a subgroup analysis of ORR by prior radiotherapy (Yes vs No) will be performed.

6.2. TIME POINT CONVENTIONS

6.2.1. STUDY DAY CONVENTIONS

Start of study treatment will use the date of first dose of tazemetostat.

Depending on the context, listings may present assessments in terms of ‘Study Day’ label where the first day of treatment is identified as ‘Day 1’ and the day prior to the first day of treatment is identified as ‘Day -1’ (with no intervening 0). Study Day will be calculated as follows:

- Assessment date \geq first dose date: Study Day = (assessment date – first dose date) + 1
- Assessment date < first dose date: Study Day = (assessment date – first dose date)
- Assessment date > last dose date: Study Day = (assessment date – last dose date);
Displayed as “## days post tx”.

Study Day will appear as missing in the listings if the event date is partial.

6.2.2. BASELINE ASSESSMENTS

Baseline is defined as the last non-missing (including unscheduled) assessment prior to starting study drug. Unless the collection time or label indicates otherwise, assessments performed on the same day as the first dose of tazemetostat will be considered as performed prior to treatment. AEs and medications with a start date on the date of first dose of tazemetostat will be considered to have occurred after the start of treatment. Baseline will be determined separately for each laboratory analyte.

